Postoperative Care: In the Post Anesthetic Care Unit (PACU) patients will receive standard care, including analgesic or antiemetic therapy as prescribed by the Attending Anesthesiologist based on his opinion of the clinical needs of the situation. When awake, the patients will be asked to rate their pain and nausea on both scales (VAS and FPS for pain, VAS and BARF for nausea). The order of presentation of scales will be the same as in the preoperative area. If a child receives analgesic or antiemetic therapy, he/she will be asked to rate the pain and nausea immediately before receiving the drug and 30-60 minutes after receiving treatment. In summary, patients will rate their pain and nausea using the VAS and the FPS-R for pain and the VAS and BARF scales for nausea at these time points: (1) before induction of anesthesia, (2) when awake in the PACU, (3) just before and (4) 30-60 mins after receiving analgesic or antiemetic therapy. The order of presentation of scales will be randomized but the same for all time points for an individual subject. After the first assessments are done in the PACU, patients will also be asked to rate their nausea on a 5 point Likert scale as: (1) Much worse than before, (2) A little worse than before, (3) The same as before (4) A little better than before and (5) Much better than before. They will also be asked if they want any treatment of their nausea. Another set of assessments will be done just prior to discharge. All other aspects of patient management will be the standard care given to such children at the Texas Children's Hospital. Patients will be discharged from the PACU when they have achieved the standard criteria set for discharge at the TCH. At the time of discharge we will give the parents a diary to record the the MAXIMUM nausea on the VAS and BARF scales and mail it back in a stamped envelope. We will phone them about 24 hours after surgery and ask if the child had any nausea, vomiting and what medications were used after going home. We will ask the parent to rate their satisfaction with the control of nausea and with the entire perioperative experience on a 0-10 scale. We will remind them to mail the nausea assessments back and to state which face represented the maximum nausea after discharge.

Section G: Sample Size/Data Analysis

G1. Sample Size

How many subjects (or specimens, or charts) will be used in this study?

Local: 240 Worldwide: 240

Please indicate why you chose the sample size proposed:

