The power analysis was calculated conservatively for the following hypotheses:

Hypothesis 1: Nausea scores on the BARF and VAS scales would be lower in children after the administration of an antiemetic. A reduction in the VAS by 2 cms and by 1 face on a faces scale is considered a clinically important reduction in symptoms. (13) Assuming that the SD of nausea on the VAS scale in children is similar to that in adults (2.5 cm) (14), a sample size of 27 would have a 90% power at the 0.01 level of significance in detecting a 2.0 cm difference in the VAS following antiemetic therapy. Hypothesis 2: Children who received rescue antiemetics in the postoperative period will have higher postoperative nausea scores on the BARF and VAS scales than those who did not receive rescue antiemetics. In addition, children who required rescue antiemetics will have higher nausea scores at the time they received the rescue drug in the postoperative period than before they developed nausea. In other words, nausea scores in the postoperative period will be higher than scores prior to induction of anesthesia in children who received rescue antiemetics. (12) The power analysis for hypothesis 2 is similar to that for hypothesis 1, and a sample size of 27 would have a 90% power at the 0.01 level of significance in detecting a 2.0 cm difference in the VAS.

Hypothesis 3: There will be a good correlation between the BARF and VAS scores for nausea. A sample size of 127 would be estimated for an estimated maximum r of 0.8, a half-width of the confidence interval of ± 0.1 at an alpha of 0.01. (15) These estimates of r are in keeping with previous studies of the correlation between

pain scores on the VAS and the FPS-R scales. (6)

Allowing for a 10% rate of dropouts and incomplete data, we plan to recruit 240 patients in the preoperative area for the study to obtain data to test all hypotheses.

G2. Data Analysis

Provide a description of your plan for data analysis. State the types of comparisons you plan (e.g. comparison of means, comparison of proportions, regressions, analysis of variance). Which is the PRIMARY comparison/analysis? How will the analyses proposed relate to the primary purposes of your study?

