Visual analogue scores for pain and for nausea, and FPS-R scores for pain and BARF scores for nausea will be examined for normal distribution by the Kolmogorov-Smirnov test, but it is anticipated that the distribution will not be normal. Descriptive statistics (mean, median, standard deviation, and frequency distribution) of the nausea and pain scores will be obtained. The incidence of postdischarge nausea will be determined from the responses recorded in the diary and in the follow up phone call. The construct validity of the BARF scale would be assessed using the assumption that antiemetics reduce nausea and therefore nausea scores would be lower in children after the administration of an antiemetic (hypothesis 1). A subgroup of patients who received rescue antiemetics in the PACU will be examined. The pretreatment and post treatment VAS scores for nausea and BARF scores will be compared using a Wilcoxon test for non Gaussian distributed data. A reduction of scores by 2 cm on the VAS scale for nausea is traditionally accepted as a clinically satisfactory therapeutic response. A significant reduction in the BARF scores by 1 face in such patients will be accepted as construct validation. Content validity would be assessed by testing the hypothesis is that children with nausea will score higher on these scales than children without nausea (hypothesis 2). We will compare the postoperative nausea scores in patients who received rescue antiemetic therapy with the scores in patients who did not require this therapy using the Mann Whitney test. In addition, we will compare preoperative and postoperative BARF and VAS scores for nausea in patients who received antiemetics, making the assumption that healthy children will be free from nausea in the preoperative area. The Wilcoxon test for non Gaussian distributed data will be used for this comparison. Convergent validity would be tested by examining the correlation between BARF and VAS scales for nausea using the Spearman's Rho test. The hypothesis tested is that there would be a good correlation between the two scales (hypothesis 3). Discriminant validity would be tested by examining the relationship between pain and nausea. The hypothesis tested is that there would be a poor correlation between pain and nausea scores, particularly after the administration of opioids for analgesia (hypothesis 4). The correlation between (1) VAS scores for pain and nausea and (2) pain scores using the FPS-R scale and nausea scores using the BARF scale will be determined. Discriminant validity would be accepted if the correlation between these scores is not as good as the correlation between (a) VAS score for pain and the FPS score, (b) VAS score for nausea and the BARF score. A subgroup of patients who received analgesic therapy in the PACU will be examined. The correlation between the change in pain scores and nausea scores with analgesic treatment will be examined using the Spearman's Rho test. We can anticipate that there will be some correlations between nausea and pain as patients with pain often have concomitant nausea. However, satisfactory treatment of pain with opioids may not reduce nausea but even increase it, as nausea is a side effect of such therapy. Similarly, the correlation between the change in pain scores and nausea scores with antiemetic treatment will be examined using the Spearman's Rho test. The hypothesis tested will be accepted if the correlation of VAS and FPS-R scores will differ from the correlation between VAS scores for nausea and BARF scores. P values below 0.05 will be considered statistically significant. The minimum clinically relevant change in BARF and VAS scores for nausea will be determined by calculating the change in scores for patients who rated their nausea to be a little better than before or a little worse than before. Similarly, the scores at which a patient felt the need for rescue therapy would be determined in those subjects who responded positively to a question "Do you want any treatment for your nausea?" This will provide the threshold score for patient perception of the need for rescue therapy. The first and subsequent scores obtained from subjects who rated their symptoms as "no change from before" will be examined using an intra-class coefficient >0.7 as the criterion for test / retest reliability.

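### Hypothesis 3 is sized in G1 for a confidence interval around r = 0.8, but G2 plans only a Spearman test against zero, so significance there does not support a good BARF-VAS correlation

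*Combined protocol and SAP*

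**What the plan says.** Section G1 (Sample Size), under hypothesis 3, chooses 127 children for a planning value it calls the estimated maximum r, 0.8, with "a half-width of the confidence interval of ± 0.1 at an alpha of 0.01". It then allows 10% for dropouts and incomplete data and recruits 240, which leaves 240 × 0.9 = 216 children.

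Section G2 (Data Analysis) handles the same hypothesis differently: "Convergent validity would be tested by examining the correlation between BARF and VAS scales for nausea using the Spearman's Rho test". The claim is put in words only: "The hypothesis tested is that there would be a good correlation between the two scales (hypothesis 3"). No interval is planned for this coefficient and no value is given for good. Later in G2, after the text on hypothesis 4, comes a general rule: "P values below 0.05 will be considered statistically significant".

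Other parts of G2 do have acceptance criteria. Construct validity needs a significant fall of one face on the BARF. Test-retest reliability is judged "using an intra-class coefficient >0.7 as the criterion for test / retest reliability". Discriminant validity has a relative rule: "Discriminant validity would be accepted if the correlation between these scores is not as good as the correlation between" the two scales for the same symptom.

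Section F2 (Procedure) collects both nausea scales more than once per child, "at these time points: (1) before induction of anesthesia, (2) when awake in the PACU", and then around any treatment and before discharge. G2 does not say which of these pairs enters the correlation.

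**The concern.** The sample size and the analysis answer different questions. G1 asks how precisely a correlation near 0.8 can be estimated. The test in G2 asks whether the correlation differs from zero. Two ratings of one symptom, given by the same child at one sitting, will nearly always correlate above zero, so rejecting zero is weak evidence of convergent validity.

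Validity in Spanish-speaking children is the first objective in Section D. If significance is taken as the answer to hypothesis 3, convergent validity could be claimed on a weak association. If it is not, hypothesis 3 has no criterion, and what counts as good can be settled after the data are known. Either way, the precision behind the 127 is not used.

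**Working it through.** **Inputs.** From G1: n = 127, r = 0.8, half-width 0.1, alpha 0.01, 240 recruited, 10% loss (216 left). From G2: Spearman's rho, P < 0.05. Assumptions: two-sided tests (the documents do not say) and one pair of scores per child.

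**1. Reproduce the 127.** Fisher interval: tanh(atanh(r) ± z/√(n − 3)), with z = 2.576 for two-sided 0.01.
- atanh(0.8) = 1.0986 and 2.576/√124 = 0.2313.
- Lower limit tanh(0.8673) = 0.700; upper limit tanh(1.3299) = 0.869.

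The lower limit lies 0.1 below 0.8, so G1's figure holds as a 99% interval (the strict minimum by this formula is 128). With 216 children the interval is 0.727 to 0.855.

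**2. Allow for Spearman's rho.** With the wider standard error √((1 + r²/2)/(n − 3)), the 99% interval at 0.8 is 0.682 to 0.877 for n = 127 and 0.714 to 0.862 for n = 216. A lower limit of 0.70 then needs 167 children, still below 216.

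**3. Smallest rho that meets P < 0.05.** Critical value: t/√(n − 2 + t²).
- n = 127: t = 1.979, so 1.979/√(125 + 3.917) = 0.174.
- n = 216: t = 1.971, so 1.971/√(214 + 3.885) = 0.134.

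Testing at 0.01 instead raises these only to 0.228 and 0.175. The gap comes from testing against zero, not from the significance level.

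**4. An example.** Observed rho 0.18, n = 127: t = 0.18 × √(125/(1 − 0.0324)) = 2.046, P = 0.043. The 99% Fisher interval is −0.05 to 0.39. The result is significant, yet far from 0.8 ± 0.1.

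**5. How often each rule is met.** Simulation from a bivariate normal, with the true value on the Spearman scale.
- P < 0.05, true rho 0.3: about 93% of studies at n = 127 and over 99% at n = 216. At a true rho of 0.5 it is always met.
- As an illustration only, 99% lower limit of at least 0.70 (0.8 minus 0.1), n = 216. Ranges run from the Spearman to the Fisher standard error:

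| True rho | Rule met |
|---|---|
| 0.70 | at most 1% |
| 0.75 | 9–16% |
| 0.80 | 64–76% |

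Tied scores lower these rates. With a percentile bootstrap, six ordered BARF categories and 60% of children scoring zero (all assumed), the rule is met about 50% of the time at a true rho of 0.80 and n = 216, against 65% without ties.

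**The case against.** The strongest reply is that G2 nowhere says P < 0.05 accepts hypothesis 3. The significance sentence is general. The text speaks of examining the correlation, so rho will be estimated and any reader can see its size. A rho of 0.18 between two nausea ratings made at one sitting is also far from the planning value, and nothing in the documents suggests it.

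Much of this stands. A reader might infer that the study cannot show a good correlation; that goes too far, because the limit lies in the test and not in the data. A reader might also infer that P < 0.05 is the declared acceptance rule; it is only the one stated rule that can reach this hypothesis. What remains is that G2 offers no other criterion and drops the interval for which G1 was sized.

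A further tempting inference is that a weak BARF-VAS coefficient would make discriminant validity easier to accept. The documents imply the reverse. The pain-nausea correlation has to fall below the BARF-VAS correlation, so a weak value lowers that ceiling and makes the criterion harder to meet.

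It is also fair to say that 0.70 is not the plan's pass mark. G1 calls 0.8 a maximum, and a rule with a lower limit of 0.70 would usually deny the label to a scale whose true rho is 0.75. That argues against imposing this value, not against stating one in advance.

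**Conclusion.** The point holds as a mismatch between G1 and G2. Hypothesis 3 is sized for a 99% interval of about ±0.1 around 0.8, but its planned test is met by an observed rho of 0.174 with 127 children or 0.134 with 216. Significance on that test does not support a good correlation; the estimate with its interval could.

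The result rests on a two-sided test and one pair of scores per child. A one-sided test would lower the critical values further, to 0.147 and 0.112. The sample size is not in question: 216 children are enough for the intended precision, even with the wider Spearman standard error.

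**What to change.** In G2, base hypothesis 3 on the estimate instead of the P value:

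- Report Spearman's rho between BARF and VAS nausea scores with its 99% confidence interval, the level used in G1. A bootstrap over children is one suitable method and copes with tied scores.
- Name in advance the one pair of ratings per child that enters the analysis.
- State, with reasons and before the data are seen, the value against which the interval will be judged for the correlation to be called good. The sponsor should choose it. A lower limit of 0.70 is one option, with the pass rates shown in the working.
- If the criterion is missed, report rho and its interval without the label.

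The cost is a few sentences. Recruitment and data collection do not change. The real price is that good becomes harder to claim, and how much harder depends on the value chosen.

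### The hypothesis 4 rule accepts discriminant validity on any numerical shortfall, with no interval or test for the difference and no value for a poor pain–nausea correlation

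*Combined protocol and SAP*

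**What the plan says.** All of this is in G2, Data Analysis, of the combined protocol and SAP, unless another section is named.

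- **The hypothesis.** "The hypothesis tested is that there would be a poor correlation between pain and nausea scores", particularly after opioids. No number defines *poor*.
- **The correlations judged.** There are two, each within one response format: "1) VAS scores for pain and nausea and (2) pain scores using the FPS-R scale and nausea scores using the BARF scale".
- **The first acceptance rule.** "Discriminant validity would be accepted if the correlation between these scores is not as good as the correlation between" two same-symptom correlations, listed as "a) VAS score for pain and the FPS score, (b) VAS score for nausea and the BARF score". No margin, interval or test is attached. The text does not say whether each pain–nausea correlation must fall below both comparators.
- **Other material under hypothesis 4.** Changes in pain are to be correlated with changes in nausea after analgesic treatment and again after antiemetic treatment, with no acceptance limit. A closing sentence compares the two same-symptom correlations with each other, so no pain–nausea correlation enters it.
- **Sample size (G1).** Hypotheses 1 to 3 are covered and hypothesis 4 is not. The benchmark for a same-symptom correlation comes from hypothesis 3: "A sample size of 127 would be estimated for an estimated maximum r of 0.8", with "a half-width of the confidence interval of ± 0.1 at an alpha of 0.01".

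In contrast, G2 does give test–retest reliability a numerical pass mark, an intraclass coefficient above 0.7.

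**The concern.** The hypothesis is that the correlation is poor. The rule asks only that it be lower than two others. These are different claims, and the second can be true when the first is plainly false. The rule also compares sample correlations from the same children as if they were known exactly, so 0.79 against 0.80 counts as acceptance.

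Validity of the scale in Spanish-speaking children is the first objective in Section D, and G2 itself expects pain and nausea to occur together. Overlap with pain is therefore a real threat to interpreting BARF. A conclusion of discriminant validity from this rule could reflect chance, or could coexist with heavy overlap.

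**Working it through.** **Inputs.**
- Same-symptom correlation 0.80: the G1 planning value for BARF with nausea VAS. G1 supports it from earlier work on pain VAS with FPS-R, so it is used here for both pairs.
- Evaluable children: 240 × 0.90 = 216, one set of four ratings each.
- Pain–nausea correlation: the documents give none, so a range is shown. Every value is an assumption.

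**1. The plan's own figure.** For r = 0.80, Fisher's z = atanh(0.80) = 1.0986. At n = 127 the standard error is 1/√124 = 0.0898, and 2.576 × 0.0898 = 0.2313. The 99% limits are tanh(1.0986 − 0.2313) = 0.700 and tanh(1.0986 + 0.2313) = 0.869. The lower arm is 0.100, so 127 is reproduced if the half-width means the lower arm (128 without rounding). At n = 216 the limits are 0.727 and 0.855. An observed 0.75 lies inside both intervals, yet against 0.80 the rule treats it as a pass.

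**2. What the rule lets through.** With all four comparisons required, it passes when both pain–nausea correlations are below the smaller same-symptom correlation. If that is 0.80, then 0.70 passes (0.70² = 49% shared variance of ranks) and so does 0.75 (0.75² = 56%). If it is 0.70, anything just under 49% passes; if 0.60, anything just under 36%.

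**3. How often it accepts.** Simulated normal scores, Spearman correlations, n = 216:

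| Same-symptom | Pain–nausea | All four comparisons | FPS-R–BARF against nausea VAS–BARF only |
|---|---|---|---|
| 0.60 | 0.60 | 11–12% | 50% |
| 0.80 | 0.80 | 10% | 51% |
| 0.80 | 0.78 | 41% | 76% |
| 0.80 | 0.75 | 83% | 95% |
| 0.80 | 0.70 | 99% | over 99% |
| 0.80 | 0.70 same format, 0.65 cross format | 98–99% | over 99% |

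The first two rows have no discrimination at all. At n = 127, a pain–nausea correlation of 0.70 is accepted 95% of the time and 0.75 is accepted 69% of the time (all four comparisons).

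**4. Adding an interval for the difference.** The rule now requires child-level bootstrap 95% intervals above zero.
- No discrimination: acceptance falls to about 0% for all four differences, and to 5% or less for one.
- Same-symptom 0.80 against 0.30–0.40: acceptance stays at about 100%.
- Same-symptom 0.80 against 0.70/0.65: about 46% for all four and 81% for FPS-R–BARF against nausea VAS–BARF. A repeat of 300 simulated studies gave 44% and 76%.
- An analytic test of dependent correlations (Meng–Rosenthal–Rubin), with every pain–nausea correlation at 0.70, gives 63% and 86%.

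The interval removes chance acceptance but does not establish that a correlation is poor.

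**5. Adding a ceiling.** Suppose the upper 95% limit must be below 0.50, an illustrative value. The largest observed correlation that passes is tanh(atanh(0.50) − 1.96/√213) = tanh(0.5493 − 0.1343) = 0.39. With that limit on BARF with pain VAS, acceptance is about 80% at a true 0.35 and about 55% at 0.40 under the normal model.

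**The case against.** **A relative comparison is a recognised form of discriminant evidence.** This stands. The fault is that it decides the hypothesis with no allowance for sampling error and no value for *poor*.

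**The general sentence setting significance at P below 0.05 might cover the rule.** It names no test for it, and step 4 shows that a difference test would still often pass 0.70.

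**A reader might infer that this is the plan's only check that BARF is not rating pain.** The documents do not support that. The change-score correlations after analgesic and antiemetic treatment are planned, and hypothesis 1 (scores fall after an antiemetic) also bears on it. However, the change-score correlations carry no pass mark, so they do not repair the rule.

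**A reader might infer that same-format pain–nausea pairs make the rule lenient.** The opposite is likelier. A shared format tends to raise those correlations, and F1 describes this carry-over, so setting them against cross-format same-symptom pairs is the stricter comparison. Replacing FPS-R with BARF by pain VAS with BARF would weaken the check.

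**The size depends on assumptions.** This stands. G1 calls 0.80 a maximum, and G2 expects non-normal scores. If 70% of nausea scores were zero (an assumption), the 0.80/0.70/0.65 case would give observed pain–nausea correlations of about 0.51–0.55, or 26–31% shared rank variance, with acceptance about 91%. With 60% at the floor and six-category faces (also an assumption), acceptance is 79% for all four. The rule stays permissive, but the one-half figure does not hold there.

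**Conclusion.** The concern holds in this form: the first hypothesis 4 rule can declare discriminant validity when the pain–nausea correlation is not poor, and it has no protection against chance. Nothing else in the plan supplies the missing interval or number.

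With no discrimination, false acceptance is about 11% if all four comparisons must hold. That is the natural reading of two correlations set against two comparators. The 50% figure applies only if a single comparison is read in. Acceptance of about 99% at 0.80 against 0.65–0.70 rests on normal scores, 216 children and same-symptom correlations at the planning maximum.

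A reader might go further and conclude that BARF will in fact share half its variance with pain. The documents give no expected pain–nausea correlation, so this shows what the rule would tolerate and is not a forecast. Nor do they support any particular ceiling; 0.50 is used only as an illustration.

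**What to change.** Reword the first rule in G2:

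1. Accept discriminant validity only if the child-level bootstrap 95% intervals lie above zero for all four differences: each same-symptom correlation (nausea VAS–BARF, pain VAS–FPS-R) minus each planned pain–nausea correlation (VAS–VAS, FPS-R–BARF).
2. Keep FPS-R with BARF in the rule. Add BARF with pain VAS as a supporting contrast, since F2 already has both collected at the same time points.
3. Then choose one of two courses. Either report the pain–nausea correlations with 95% intervals and conclude only that they are lower than the same-symptom correlations, or have the investigators fix and justify a ceiling for *poor* before seeing the data, with the upper 95% limit required to fall below it.

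**Cost.** A change of wording and a short bootstrap, with no new data. The chance of acceptance falls when the correlations are close, which is intended. A ceiling costs more. With the illustrative 0.50 on BARF with pain VAS, roughly one study in five fails at a true 0.35 and nearly half fail at 0.40. The investigators should weigh this, because G2 already anticipates some correlation between pain and nausea.

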Intraoperative Care After providing baseline values in the preoperative holding area, the patient's anxiety would be assessed using the validated modified Yale Preoperative Anxiety scale (mYPAS) [see attachment], while the child is in the holding area, at the time of separation and when the face mask is applied during induction of anesthesia. The child would receive general anesthesia. The choice of drugs, techniques and perioperative management, including the need (if any) for preoperative medication, will be determined by the Attending Anesthesiologist according to the clinical needs and will not be changed for the purposes of the study. The patient will be monitored in keeping with the standards and policies of the department of Anesthesiology, Texas Children's Hospital. We will record these drugs, techniques and perioperative management.

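### The opioid clause of hypothesis 4 is examined only in a subgroup defined by any PACU analgesic, with no split by opioid use

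*Combined protocol and SAP*

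**What the plan says.** All of hypothesis 4 sits in section G2 (Data Analysis) of the combined protocol and SAP. The prediction is that "there would be a poor correlation between pain and nausea scores, particularly after the administration of opioids for analgesia".

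Two analyses follow.

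- **Main test.** Pain is correlated with nausea on the two VAS scales and on the FPS-R and BARF scales. The rule begins "Discriminant validity would be accepted if the correlation between these scores is not as good as the correlation between" and goes on to name the two same-symptom correlations. No restriction to children given an analgesic or an opioid is stated.
- **Supporting analysis.** "A subgroup of patients who received analgesic therapy in the PACU will be examined", and then "The correlation between the change in pain scores and nausea scores with analgesic treatment will be examined using the Spearman's Rho test". No threshold or acceptance rule is attached to this coefficient.

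The reason offered for the supporting analysis is that "satisfactory treatment of pain with opioids may not reduce nausea but even increase it, as nausea is a side effect of such therapy". The sentence before it concedes that some pain-nausea correlation is to be expected, because the two symptoms often occur together.

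On drug choice, section F2 (Postoperative Care) says that children receive "analgesic or antiemetic therapy as prescribed by the Attending Anesthesiologist based on his opinion of the clinical needs of the situation". On data capture, F2 (Intraoperative Care) says "We will record these drugs, techniques and perioperative management". No analysis in G2 is restricted to, or split by, opioid use.

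**The concern.** The reasoning behind the change-score analysis depends on drug class. Pain and nausea may ease together when pain is relieved. An opioid is expected to break that link, because it can relieve pain while leaving nausea unchanged or worse. The plan then computes one coefficient over everyone given any analgesic.

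This has two consequences.

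- The opioid clause is comparative: the correlation should be poor in general and poorer still after opioids. A single pooled coefficient cannot show that.
- If the subgroup contains both kinds of treatment, the pooled value depends partly on local prescribing. The same behaviour of the BARF scale could give a visibly positive coefficient in one case mix and a near-zero one in another.

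At stake is one stated component of a numbered hypothesis, and the interpretation of one supporting analysis.

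**Working it through.** **No figure to reproduce.** Section G1 sizes the study for hypotheses 1 to 3 only. For hypothesis 4 the documents give no sample size, expected correlation, subgroup size or opioid share. What follows is an illustration on assumed inputs.

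**Inputs from the documents**
- Subgroup: any PACU analgesic (G2).
- Statistic: Spearman's rho of change in pain against change in nausea (G2).
- Drug class: open, at the attending's discretion (F2).
- Prediction after opioids: poor correlation (G2), taken here as 0.

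**Assumed inputs**
- Bivariate normal changes, with the same marginal distributions in both drug groups.
- Correlation r = 0 after opioids, and r = 0.2, 0.4 or 0.6 after non-opioids.
- Opioid share p = 90%, 70%, 50% or 30%.

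**Formula.** With equal marginal distributions, Spearman's rho of a mixture is the share-weighted average of the group values:

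pooled rho = p × S(r after opioids) + (1 − p) × S(r after non-opioids), where S(r) = (6/π) × arcsin(r/2) for normal data.

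S(0) = 0, so pooled rho = (1 − p) × S(r after non-opioids).

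- S(0.2) = 1.910 × 0.1002 = 0.191
- S(0.4) = 1.910 × 0.2014 = 0.385
- S(0.6) = 1.910 × 0.3047 = 0.582

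For r = 0.4 and p = 90%: 0.10 × 0.385 = 0.038. For p = 30%: 0.70 × 0.385 = 0.269.

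**Results** (formula, with a simulation of 400,000 draws in brackets)

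| Opioid share | r = 0.2 | r = 0.4 | r = 0.6 |
|---|---|---|---|
| 90% | 0.019 (0.021) | 0.038 (0.040) | 0.058 (0.060) |
| 70% | 0.057 (0.057) | 0.115 (0.114) | 0.175 (0.177) |
| 50% | 0.096 (0.095) | 0.192 (0.196) | 0.291 (0.290) |
| 30% | 0.134 (0.135) | 0.269 (0.266) | 0.407 (0.410) |

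In every cell the opioid correlation is exactly 0, so the whole pooled value comes from non-opioid cases.

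**Sensitivity to equal marginals.** Raising the nausea change by 0.5 SD in the opioid group, with r = 0.4, gives simulated values of 0.036, 0.110, 0.187 and 0.266 for shares of 90%, 70%, 50% and 30%. The picture does not change.

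**Price of splitting.** Interval width scales roughly with 1/√n, so the opioid stratum's interval is wider than the pooled one by about 1/√p:
- 90%: 1/√0.9 = 1.05
- 70%: 1/√0.7 = 1.20
- 50%: 1/√0.5 = 1.41
- 30%: 1/√0.3 = 1.83

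**The case against.** The strongest reply is that this is a minor matter in an analysis on which nothing depends. Hypothesis 4 is general: *particularly* adds an emphasis and does not restrict it to opioids. It is tested in the main analysis, which carries no analgesic restriction and has its own acceptance rule. A second acceptance sentence at the end of the hypothesis 4 text compares the two same-symptom correlations. Neither rule uses the change-score coefficient. All of this stands, and it limits the point to the opioid clause.

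Two stronger readings are tempting, and the documents support neither.

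- A reader might infer that hypothesis 4 as a whole is tested in the wrong children. It is not, because the main test is not confined to children given an analgesic and mixing drug classes in the subgroup does not touch it.
- A reader might infer that opposite correlations in the two drug groups could cancel and give a spuriously low pooled value. That needs a negative correlation after opioids. The plan predicts a poor one. A general rise in nausea after opioids concerns its average level and does not imply that individual changes are negatively correlated. With a value near 0 after opioids, pooling dilutes and does not cancel.

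It is also fair to say that mixing is possible rather than certain. F2 leaves drug class open, but no section names a non-opioid PACU analgesic or gives a share. If nearly all children receive opioids, the effect is small (0.02 to 0.06 at 90%).

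Finally, a split by PACU drug is imperfect. A child given only a non-opioid in the PACU may have had an opioid during surgery, and the sentence on recording drugs stands under Intraoperative Care. Both caveats stand and are carried into the fix. They do not supply the missing analysis of the opioid clause.

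**Conclusion.** The point holds in a limited form. The opioid clause of hypothesis 4 is approached only through a coefficient pooled over all PACU analgesics, so it is not isolated, although the reason given for the analysis is opioid-specific. If non-opioids are used, the pooled rho partly reflects the drug mix: about 0.04 to 0.27 across opioid shares of 90% to 30%, if the correlation is 0 after opioids and 0.4 after non-opioids. Over the wider range of 0.2 to 0.6 after non-opioids, it runs from 0.02 to 0.41. The correlations and the share are assumptions.

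The conclusion on discriminant validity under the plan's own acceptance rule is not at risk. This is a cheap improvement to a supporting analysis.

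**What to change.** In G2, make these changes to the change-score analysis and leave the main discriminant-validity test and its acceptance rule as they are.

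1. Report the correlation of change in pain with change in nausea separately for children whose PACU analgesic included an opioid and for those given only non-opioids, each with a confidence interval.
2. Name the opioid stratum as the examination of the opioid clause only, not of hypothesis 4 as a whole, with the non-opioid stratum as its contrast.
3. Report the pooled coefficient descriptively.
4. Confirm that the class of each PACU analgesic is recorded.
5. Describe intraoperative opioid use in both strata, since it may blur the contrast.

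The cost is a few sentences in G2 and a check of the data form. Care, assessments and recruitment do not change. The statistical price is the wider interval in the opioid stratum: about 5% wider than the pooled one at a 90% share and about 41% wider at 50%. The non-opioid stratum may be small, in which case its interval will show how little can be said.
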